8.3.7 TIME PERIOD AND FREQUENCY FOR EVENT ASSESSMENT AND FOLLOW-UP

The occurrence of an adverse event (AE) or serious adverse event (SAE) may come to the attention of study personnel during study visits and interviews of a study subject presenting for medical care, or upon review by a study monitor. All AEs will be captured on the appropriate eCRF as noted above in section 8.2.

Any medical condition that is present at the time that the subject is initially screened will be considered as pre-existing and not reported as an AE. However, if the study subject’s condition deteriorates at any time during the study, it will be recorded as an AE.

Changes in the severity of an AE will be documented to allow an assessment of the duration of the event at each level of severity to be performed. AEs characterized as intermittent require documentation of onset and duration of each episode.

The study Investigator will record all reportable events with start dates occurring any time after informed consent is obtained the last day of study participation (i.e., Follow-Up Visit 2). At each study visit, the investigator will inquire about the occurrence of AE/SAEs since the last visit. Events will be followed for outcome information until resolution or stabilization.

If an AE is not resolved by the end of the study, that event will be marked as such by the Investigator.

8.3.8 ADVERSE EVENT REPORTING

Adverse events will be reported to the Sponsor using the eCRFs in the EDC as the Investigator becomes aware of them. The Investigator is responsible for reporting any and all adverse events to their federal, state, and local oversight committees (e.g., IRBs) as required by that committee.

Adverse reactions to the AMNIOEXCEL Plus must be reported within 2 business days to the Sponsor (Integra) via the AE eCRF in the EDC system. *Important note: Subject records must be maintained for the purpose of tracing tissue post-transplant per The Joint Commission on Accreditation of Healthcare Organizations and FDA requirements. The AMNIOEXCEL Plus ID number must be recorded in the recipient's medical record. Patient labels which include tissue numbers are contained in the AMNIOEXCEL Plus package to aid in the tracking process.*

8.3.9 SERIOUS ADVERSE EVENT REPORTING

Investigators are instructed to report SAEs to Integra within 10 business days of the Investigator becoming aware of the SAE.

SAEs must be reported by the Investigator to Integra by completing the SAE eCRF. All SAEs and deaths that are possibly related, probably related, or definitely related to the investigational product or study procedures must be reported. The information collected will include a minimum of the following: subject number, a narrative description of the event, lot number of device used on subject, and an assessment by the Investigator as to the intensity of the event and relatedness to study device. Follow-up information on the SAE may be requested by the Sponsor.

Any subjects reporting SAEs that have not resolved by their last treatment visit will be followed via phone or clinic visit through resolution or 14 days post final visit, whichever comes first.

8.3.10 UNANTICIPATED SERIOUS ADVERSE EVENT REPORTING

Investigators are instructed to report UNANTICIPATED SADEs to Integra AND to the IRB, if required, within 10 business days of the Investigator becoming aware of the SAE. *NOTE: Local IRBs may require different timelines and/or reporting requirements. Each Investigator approved to conduct research under the authority of a local IRB is responsible for knowing these requirements and for abiding by them.*

9 STATISTICAL CONSIDERATIONS

This section presents general information about statistical methodologies and concepts for this study. Further technical details (e.g., statistical analysis methods and data conventions) will be provided in the Statistical Analysis Plan (SAP).

9.1 STATISTICAL ENDPOINTS

- Primary Efficacy Endpoint(s):

The primary endpoint of this study is the incidence of complete wound closure, as assessed by the Investigator at or before Week 12 of the Treatment Phase and confirmed closed 2 weeks later. Confirmed complete wound closure is defined as complete skin re-epithelialization that is without drainage or dressing requirements two weeks later.

A subject is considered to have a closed wound (i.e., a closure success) if the subject's treated wound closes between week 1 and 12 and is noted as closed on both follow-up visits.

A subject is considered to not have a closed wound (i.e., a closure failure) if they meet any of the following:

- the subject's treated wound does not close by week 12
- the subject's treated wound closes between week 1 and 12 and is noted as open on either or both of the follow-up visits.

A subject is considered to have an undetermined wound closure if the subject's treated wound closes between week 1 and 12 and the subject misses either or both of the follow-up visits. These subjects may become part of extended analyses.

- Secondary Efficacy Endpoint(s):
 1. Proportion of subjects with complete closure of the study ulcer at or before Week 12 as assessed by computerized planimetry.
 2. Proportion of subjects with complete wound closure of the study ulcer at or before Week 12 as assessed by independent, blinded, assessment of photographs.
 3. Time to complete wound closure, as assessed by the Investigator.
 4. Time to complete wound closure, as assessed by computerized planimetry.
 5. Rate of wound closure, as assessed by computerized planimetry.
 6. Medical resource utilization associated with treatment of DFU and related complications as determined by a comparison of estimated costs from the presumed billing codes which would have been used for each patient.

9.2 SAMPLE SIZE DETERMINATION

A total of 114 subjects, 38 per cohort, will be enrolled, inclusive of a 20% in-study attrition rate.

It is assumed that the maximum wound closure rate is 90% with no difference between the study cohorts. Based on the 38 subject per cohort sample size, the half width of the 95% confidence interval for the wound closure rate is 13.5%. However, the study is not adequate for hypothesis testing.

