9.5. Missing Data

For primary efficacy evaluation of data points, the last available observation (LOCF) will be used. In the analyses of using the planimetry data, the last available planimetric value will be used for a discontinued subject. All subjects discontinued during the treatment period and before 100% wound closure during the treatment phase of the study will not be replaced and will be considered treatment failures for evaluating the primary and secondary endpoints.

10. Description of Other Variables and Analyses

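### The stated 13.5-point half-width is a best case: it fits a between-arm difference at 90% closure, a rate that the plan's own attrition and failure rules make hard to reach

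*Protocol*

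**What the plan says.** Protocol 9.2 sets the size: "A total of 114 subjects, 38 per cohort, will be enrolled, inclusive of a 20% in-study attrition rate". It then gives the assumption behind the precision figure, "It is assumed that the maximum wound closure rate is 90% with no difference between the study cohorts", and the result, "Based on the 38 subject per cohort sample size, the half width of the 95% confidence interval for the wound closure rate is 13.5" (per cent). It adds: "However, the study is not adequate for hypothesis testing". The synopsis and SAP 5 repeat the paragraph in nearly the same words. None of the three gives a source for 90%, and none says how the 20% attrition affects the half-width.

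The analysis rules are elsewhere. The primary population is all randomized subjects with at least one application (Protocol 9.3, SAP 8.1), so treated dropouts stay in the denominator. Missing primary data are handled by last observation carried forward (Protocol 9.4.5, SAP 9.1). Under SAP 9.5, subjects who discontinue in the treatment period before closure "will not be replaced and will be considered treatment failures for evaluating the primary and secondary endpoints". Subjects who close but miss a confirmation visit are classed as undetermined, neither success nor failure (Protocol 9.1, SAP 9.1). SAP 11.1.1 specifies Clopper-Pearson intervals for one proportion and a continuity-corrected Z interval for a difference.

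**The concern.** The plan disclaims hypothesis testing, so this half-width is the only quantitative support for 114 patients. Two things about its input look wrong. First, the variance of a proportion shrinks towards the extremes, so a maximum closure rate of 90% produces a minimum half-width, yet the result is stated as the precision of the trial. Second, the calculation uses all 38 subjects and a 90% rate together, while the same paragraph expects 20% attrition. Dropouts who are kept and scored as failures lower the rate, and dropouts who are excluded lower n. Either way the stated figure is hard to reach. The plan reports between-arm differences with 95% intervals as part of the primary analysis, and readers would expect those intervals to be narrower than the design is likely to give.

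**Working it through.** **Inputs.** n = 38 per arm, attrition 20%, closure rate p = 0.90 in every arm, 95% two-sided (Protocol 9.2, SAP 5). Interval methods are from SAP 11.1.1 and the failure rule from SAP 9.5.

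**1. Reproduce the stated figure.** Uncorrected Wald half-width for a difference between two arms with equal rates:

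1.96 × √(2 × 0.90 × 0.10 / 38) = 1.96 × 0.0688 = 13.5 points.

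This matches. The label refers to the closure rate itself, but no single-rate method tried at n = 38 and 90% gives 13.5: Wald 9.5, Wald with continuity correction 10.9, Wilson 9.8, Agresti-Coull 10.4, Clopper-Pearson 10.9 (34 of 38).

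**2. Where 90% sits.** p(1−p) is 0.09 at 90%, 0.16 at 80%, 0.20 at 72% and 0.25 at 50%. Every rate strictly between 10% and 90% gives a wider Wald interval than 90% does. This step does not depend on attrition.

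**3. What attrition does to the rate.** Suppose the 20% leave before closure.

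- Ceiling: 1 − 0.20 = 0.80.
- If 90% is the rate among completers: 0.90 × 0.80 = 0.72.

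Carrying forward the last observation of an open wound gives the same classification as the SAP 9.5 failure rule, so these figures do not depend on which of the two is applied.

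**4. What if some leave after closure?** Let f be the share of dropouts who leave after closure and are counted as closed. An overall 90% then requires completers to close at (0.90 − 0.20f)/0.80. That exceeds 100% for f below 0.5, is 100% at f = 0.5 and is 87.5% at f = 1. So 90% needs at least half the dropouts to have closed first and to be counted as successes.

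If instead all dropouts are of this kind and are excluded as undetermined, n is 38 × 0.80 = 30.4, about 30. The uncorrected half-width for the difference is then 1.96 × √(0.18/30) = 15.2 points even at 90%.

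**5. Half-widths at n = 38, in percentage points.** The continuity correction adds ½(1/38 + 1/38) = 2.6 points. Clopper-Pearson values are half the full interval width at 34, 30, 27 and 19 closures of 38.

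| Closure rate | Difference, uncorrected Wald | Difference, continuity-corrected | One arm, Clopper-Pearson |
|---|---|---|---|
| 90% | 13.5 | 16.1 | 10.9 |
| 80% | 18.0 | 20.6 | 13.9 |
| 72% | 20.2 | 22.8 | 15.2 |
| 50% (assumed worst case) | 22.5 | 25.1 | 16.6 |

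**6. Size of the shortfall.**

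- Uncorrected difference: 1 − 13.5/18.0 = 25% at 80%, 1 − 13.5/20.2 = 33% at 72%, 1 − 13.5/22.5 = 40% at 50%.
- One arm, Clopper-Pearson: 13.5 is wider than needed at 90% (10.9). It is 1 − 13.5/13.9 = 3% short at 80%, 1 − 13.5/15.2 = 11% at 72% and 1 − 13.5/16.6 = 19% at 50%.

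**The case against.** The strongest reply is that the documents label 13.5 as the half-width for a closure rate, not for a difference. On that wording the figure is generous at 90% and almost right at 80%; single-arm Wald at 80% is 12.7, inside the stated value. A reader might infer that the trial must be less precise than stated whatever the figure means, and the literal label does not support that. What remains is that the stated inputs do not produce 13.5 as a single-rate figure, so the label cannot rescue the calculation.

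A reader might also treat 80% as a hard ceiling. It is not one. It assumes that all attrition is in treated subjects before closure. The documents leave open whether a subject who closes and then misses a confirmation visit is carried forward as closed or left out, and Protocol 7.2 allows replacement of subjects randomized but never treated. Nor does reaching 90% always require every completer to close, since that holds only when exactly half the dropouts leave after closure.

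Finally, the plan does call 90% a maximum and does disclaim hypothesis testing. No power statement or decision rule depends on 13.5, and the observed intervals will be reported whatever this paragraph says. That limits the consequence. But the disclaimer concerns power, and calling the rate a maximum does not tell the reader that the resulting half-width is a minimum.

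**Conclusion.** The concern holds in a limited form. The stated 13.5 points is the uncorrected Wald half-width for a between-arm difference at 90% closure with all 38 subjects per arm, and it is the most favourable value for any rate from 10% to 90%. Even at 90%, the interval that the SAP specifies for a difference has a half-width of 16.1. If the 20% attrition precedes closure, the stated figure is 25% too small at the 80% ceiling and 33% too small at 72%, measured by the formula that produced it. The 40% shortfall rests on a 50% rate, which is a worst case assumed here and not taken from the documents. These percentages apply to the difference only. None of this shows that 38 per arm is the wrong size, because the plan sets no precision target that the trial would then miss. It shows that the only stated justification for the size is labelled as the wrong quantity and presented without saying that it is a best case.

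**What to change.** In Protocol 9.2, the synopsis and SAP 5, replace the single figure with a short table of half-widths at n = 38 over closure rates that the primary analysis could produce, for example 50%, 72%, 80% and 90%. Give two columns, each named: one arm by Clopper-Pearson, and the between-arm difference by the continuity-corrected Z interval, as in SAP 11.1.1. Label 90% as the best case and 50% as an assumed worst case. Add a sentence on how the 20% attrition and the failure rule enter the calculation, including whether subjects classed as undetermined count as closed, as failures, or leave the denominator.

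SAP 12 shows that the photograph review data had already been collected when that section was written. If the protocol can no longer be amended, the correction belongs in SAP 5 and the study report. The cost is a paragraph and a small table, with a less favourable stated precision. No extra patients are needed. The half-width table changes no analysis, and the sentence on undetermined subjects only settles a point the plan leaves open.

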9.4 STATISTICAL ANALYSES

9.4.1 GENERAL APPROACH

All study data collected in the eCRF will be presented in subject data listings. Statistical analyses will be performed using SAS[®] for Windows, version 9.4 or later. Descriptive statistics (n, mean, standard deviation, median, minimum and maximum) will be calculated by treatment group for continuous variables. Frequencies and percentages will be presented by treatment group for categorical variables.

Unless otherwise specified, all testing will be performed using two-sided test at the 0.05 level of significance.

9.4.2 SUBJECT DISPOSITION

The disposition of all subjects who sign an ICF will be provided. The numbers of subjects screened, randomized, completed, and discontinued during the study, as well as the reasons for all post-randomization discontinuations will be summarized by treatment group, for all sites combined and each site separately. Disposition and reason for study discontinuation will also be provided as a by-subject listing.

9.4.3 PROTOCOL DEVIATIONS

Protocol deviations will be identified and listed by study sites based on the definitions and constraints set forth in section 10.1.9 of the protocol, below.

9.4.4 BASELINE DESCRIPTIVE STATISTICS

Demographic data including but not limited to age, race, gender and ethnicity and other baseline characteristics, but not limited to medical and surgical history will be tabulated by treatment and

overall. Summarized demographic data will include mean, standard deviation, minimum and maximum; as well as analogous summary statistics for presenting diagnosis and other relevant patient characteristic factors.

9.4.5 ANALYSIS OF THE PRIMARY EFFICACY ENDPOINT(S)

The primary objective of this study is to assess the proportion of subjects who achieve complete wound closure by 12 weeks and confirmed 2 weeks later, for the Active Treatment Groups (AMNIOEXCEL Plus Placental Allograft Membrane with SOC, Apligraf bi-layered skin substitute with SOC) and Control Treatment Group (or SOC alone).

The primary analysis will be conducted on the ITT population. The proportion of subjects with confirmed closed study wound, as assessed by the investigator, will be compared between AMNIOEXCEL Plus and Apligraf, and AMNIOEXCEL Plus and SOC. The proportion of subjects with confirmed complete wound closure will be compared using the Cochran–Mantel–Haenszel (CMH) test.

For the primary efficacy analysis, missing values will be imputed using last observation carried forward (LOCF). The differences in confirmed complete wound closure rate between treatment arms will be summarized along with 95% confidence intervals.

9.4.6 ANALYSIS OF THE SECONDARY ENDPOINT(S)

The following are for exploratory analysis purposes.

Proportion of ulcers with complete wound closure during the treatment phase as assessed by planimetry will be compared using Logistic Regression with selected baseline covariates in the model.

Time to complete wound closure will be analyzed using log rank test or Cox proportional regression model. Kaplan-Meier methods will be used to present median time to complete wound closure.

Summary statistics will be provided for the rate of wound closure for the two treatment groups.

9.4.7 SAFETY ANALYSES

AEs/SAEs related to the investigational product, study ulcer and/or study procedures and will be recorded.

AEs will be coded according to the most recent version of the Medical Dictionary for Regulatory Activities (MedDRA) AE coding dictionary, and grouped by body system. The number and percentage of subjects experiencing at least one AE of any type, AEs within each body system and AEs within each preferred term will be presented for each treatment group. Separate summaries will be provided for all AEs, device related AEs, SAEs and AEs leading to withdrawal.

All safety parameters will be summarized descriptively by treatment assignment. No inferential statistics are planned.

Listings of complications will be presented, include complication type, relation to study device, relation to procedure, action taken, and clinical outcome. Separate listings will be constructed for complications with possible, probable, or definite relationship to the device, serious complications, and for all complications. The listing for all complications will be sorted by complication type.

9.4.8 PLANNED INTERIM ANALYSES

An interim analysis will occur after 50% of subjects have satisfied the primary endpoint of the study. Descriptive statistics will be provided. Primary and secondary endpoints will be evaluated at the time of interim analysis.

9.4.9 SUB-GROUP ANALYSES

Sub-group analysis is not planned for this study.

9.4.10 TABULATION OF INDIVIDUAL SUBJECT DATA

All collected study data will be presented in subject data listings. Details will be provided in SAP.

9.4.11 MULTIPLICITY ADJUSTMENT

There will be no multiplicity adjustment for primary and secondary endpoint analysis for comparing three treatment groups nor any adjustment for the planned interim analysis.

9.4.12 EXPLORATORY ANALYSES

Exploratory analyses will be performed to examine wound closure status at Week 4 of Treatment and wound closure status at the 2-week follow-up visit

Proportion of subjects with confirmed complete wound closure of the study ulcer at week 4 Treatment Phase, and at the 2-week follow-up visit as assessed by computerized planimetry for each of the treatment groups will be summarized. A point estimate will be presented along with the exact 95% confidence interval based on the binomial distribution.

[Intentionally Blank]

10 SUPPORTING DOCUMENTATION AND OPERATIONAL CONSIDERATIONS

10.1 REGULATORY, ETHICAL, AND STUDY OVERSIGHT CONSIDERATIONS

10.1.1 INFORMED CONSENT PROCESS

10.1.1.1 CONSENT/ASSENT AND OTHER INFORMATIONAL DOCUMENTS PROVIDED TO SUBJECTS

Consent forms describing in detail the study intervention, study procedures, and risks will be given to the subject and written documentation of informed consent (i.e., a signed consent form) is required prior to performing any study-related procedures.

10.1.1.2 CONSENT PROCEDURES AND DOCUMENTATION

Informed consent is a process that is initiated prior to the individual's agreeing to participate in the study and continues throughout the individual's study participation. The subject must agree to participate in the study and sign the informed consent document prior to any procedures being done specifically for the study. Consent forms will be IRB-approved and the subject will be asked to read and review the document. A verbal explanation will be provided in terms suited to the subject's comprehension of the purposes, procedures, and potential risks of the study and of their rights as research subjects. Subjects will have the opportunity to carefully review the written consent form, ask questions and discuss the study with their family/friends/surrogates prior to agreeing to participate. **Subjects must be informed that participation is voluntary and that they may withdraw from the study at any time, without prejudice.** A copy of the signed informed consent document will be given to the subjects for their records. The informed consent process will be documented in the subject's medical record and source document, the rights and welfare of the subjects will be protected by emphasizing to them that the quality of their medical care will not be adversely affected if they decline to participate in this study.

10.1.2 STUDY DISCONTINUATION AND CLOSURE

This study may be temporarily suspended or prematurely terminated if there is sufficient reasonable cause. Written notification, documenting the study suspension or termination, will be provided by the suspending or terminating party to investigator and oversight authorities (e.g., IRB). If the study is prematurely terminated or suspended by the Sponsor, the Investigators will promptly inform study subjects, the IRB. If an oversight authority (e.g., IRB) suspends or terminates a study at a site, the Investigator should notify the Sponsor within 24 hours. Study subjects will be contacted, as applicable, and be informed of changes to their visit schedule.

Circumstances that may warrant termination or suspension include, but are not limited to:

- Determination of unexpected, significant, or unacceptable risk to subjects
- Demonstration of efficacy that would warrant stopping
- Insufficient compliance to protocol requirements
- Data that are not sufficiently complete and/or evaluable
- Determination that the primary endpoint has been met
- Determination of futility

The study may resume if resolution of the suspending/terminating factor occurs.

10.1.3 CONFIDENTIALITY AND PRIVACY

Subject confidentiality and privacy is strictly held in trust by the participating Investigators, their staff, oversight authorities (e.g., IRBs), the Sponsor, and third party affiliates. This confidentiality is extended to cover all data collected within the confines of this protocol. Therefore, the study protocol, documentation, data, and all other information generated will be held in strict confidence. No information concerning the study or the data will be released to any unauthorized third party without prior written approval of the Sponsor.

All research activities will be conducted in as private a setting as possible.

The study monitor, other authorized representatives of the sponsor, representatives of the IRB, regulatory agencies or pharmaceutical company supplying study product may inspect all documents and records required to be maintained by the investigator, including but not limited to, medical records (office, clinic, or hospital) and pharmacy records for the subjects in this study. The clinical study site will permit access to such records.

The study subject's contact information will be securely stored at each clinical site for internal use during the study. At the end of the study, all records will continue to be kept in a secure location for as long a period as dictated by the reviewing IRB, Institutional policies, or sponsor requirements.

Study subject research data, which is for purposes of statistical analysis and scientific reporting, will be transmitted to the sponsor via an EDC system (Clindex®, Fortress Medical Systems). This will not include the subject's contact or identifying information. Rather, individual subjects and their research data will be identified by a unique study identification number. The study data entry and study management systems used by clinical sites and by the Sponsor's research staff will be secured and password protected. At the end of the study, all study databases will be de-identified and archived at the Sponsor's headquarters.

